A megastudy of text-based nudges encouraging patients to get vaccinated at an upcoming doctor's appointment

06/11/2021

NCT04565353

Modification

Basic Info

Confirmation Number: **ddecijgd**
Protocol Number: **843523**
Created By: **[name]**
Principal Investigator: **[name]**
Protocol Title: **Mega-study to promote flu vaccinations**
Short Title: **Mega-study to promote flu vaccinations**
Protocol Description: **We will conduct two "mega-studies" to investigate the effectiveness of at least 40 different SMS and incentive-based interventions for increasing flu vaccinations. Trial A will include primary care patients at Penn Medicine and Geisinger health systems. This project has been approved by Penn Medicine's privacy office, Information systems committee, and Executive Leadership. Trial B will include Walmart pharmacy customers who have consented to receive SMS communications from Walmart.**
Submission Type: **Social and Biological Sciences**
Application Type: **EXPEDITED Category 7**

PennERA Protocol Status

Approved (No CR)

Resubmission*

No

Are you submitting a Modification to this protocol?*

Yes

Current Status of Study

Study Status

Currently in Progress

If study is currently in progress, please enter the following

Number of subjects enrolled at Penn since the study was initiated

47601

Actual enrollment at participating centers

772628

If study is closed to further enrollment, please enter the following

Number of subjects in therapy or intervention

0

Number of subjects in long-term follow-up only

0

IRB Determination

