Primary outcome variable(s)

Trial A: The primary outcome is whether participants receive a flu vaccination at their primary care appointment. Trial B: The primary outcome is whether participants receive a flu vaccination at any time in the fall of 2020 at a Walmart pharmacy.

Secondary outcome variable(s)

Trial A: A secondary outcome is whether participants receive a flu vaccination after their primary care appointment until March 31, 2021, after receiving the intervention. Trial B: A secondary outcome is whether participants receive a flu vaccination in the before March 31, 2021.

Background

Annually, the influenza causes millions of illnesses, hundreds of thousands of hospitalizations, and tens of thousands of deaths in the United States (CDC, 2020). The most effective way to combat the flu is with an annual vaccine, which can reduce the risk of contracting the flu by 50% and the risk of hospitalization by 80% (Thompson et al, 2018). The CDC recommends that everyone over 6-months old gets an annual flu vaccination, and estimates that in the 2017-2018 flu season alone (i.e., September 2017-March 2018), the flu vaccine prevented over six million illnesses, almost 100,000 hospitalizations, and almost 6,000 deaths (CDC, 2019). Despite these benefits, each year, less than half of Americans get a flu shot (CDC, 2019), leading to unnecessary illnesses. It is estimated that a 5% increase in vaccination rates in 2017-18 would have led to as many as 25,000 fewer hospitalizations (Hughes et al, 2019).

Study Design

Phase*

Not applicable

Design

Participants will be randomly assigned to the different study conditions. Randomization may be stratified by age, clinical site, primary care provider role, and other factors. Care providers will not be aware of the intervention received by the participant.

Study duration

Trial A: Penn Medicine and Geisinger Health patients with primary care appointments from September 1, 2020 to March 31, 2021 will be included. These participants may receive intervention messages up to four days prior to their scheduled appointments. In some conditions, participants will receive additional communications after their appointment about incentives they earned. Trial B: Walmart pharmacy customers will be assigned to an intervention and may receive intervention messages over the course of 4 days at the start of the flu season. They may also receive additional messages about incentives earned after receiving a flu shot.

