Trial A: Penn Medicine and Geisinger patients will be included if they: - Have a cell phone number recorded in a Penn Medicine or Geisinger database - Have a new or routine primary care appointment during the Fall 2020 flu season (not a sick visit) Trial B: Walmart pharmacy customers will be included if they: - Have consented to receive text messages about their Walmart prescriptions - Have received a flu shot from Walmart in the past - Have been selected for study inclusion by Walmart

Key exclusion criteria

Trial A: - Has documentation of allergy or adverse event to influenza vaccination in medical records - Has documentation of already receiving their 2020 influenza vaccination prior to randomization in medical records - Has opted out of receiving text message appointment reminders - Has asked not to be contacted for research purposes - Has an appointment with someone other than their primary care physician - Has an appointment with someone other than a physician, resident, nurse practitioner, or physician assistant. Trial B: None

Vulnerable Populations

Children Form

Pregnant women (if the study procedures may affect the condition of the pregnant woman or fetus) Form

Fetuses and/or Neonates Form

Prisoners Form

Other

None of the above populations are included in the research study

The following documents are currently attached to this item:

There are no documents attached for this item.

Populations vulnerable to undue influence or coercion

Not applicable

Subject recruitment

Trial A: All eligible Penn Medicine and Geisinger patients with routine primary care appointments from September 1, 2020 to March 31, 2021 will be enrolled and randomly assigned to a study condition.

Trial B: All eligible Walmart pharmacy customers will be enrolled and randomly assigned to a study condition.

Will the recruitment plan propose to use any Penn media services (communications, marketing, etc.) for outreach via social media avenues (examples include: Facebook, Twitter, blogging, texting, etc.) or does the study team plan to directly use social media to recruit for the research?

No

The following documents are currently attached to this item:

There are no documents attached for this item.

Subject compensation*

Will subjects be financially compensated for their participation?

Yes

The following documents are currently attached to this item:

There are no documents attached for this item.

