For both trials, the primary outcome will be whether participants receive an influenza vaccination, as recorded in their medical records or customer data. For Trial A, this will include whether they tell their provider they received a vaccination prior to their appointment but after enrollment in our study, receive a vaccination at their appointment, or receive their vaccination at another appointment or location after enrollment in our study (if documented in their medical record). For Trial B, this will include whether they receive the flu shot at a Walmart pharmacy after enrollment in our study. We will use an ordinary least squares (OLS) regression of a binary vaccination receipt indicator at the individual level, adjusting for individual characteristics (e.g., demographics, comorbidities), and visit characteristics (e.g., doctor information, clinic site; Trial A only).

The following documents are currently attached to this item:

There are no documents attached for this item.

Data confidentiality

Paper-based records will be kept in a secure location and only be accessible to personnel involved in the study.

- x **Computer-based files will only be made available to personnel involved in the study through the use of access privileges and passwords.**

Prior to access to any study-related information, personnel will be required to sign statements agreeing to protect the security and confidentiality of identifiable information.

- x **Wherever feasible, identifiers will be removed from study-related information.**

A Certificate of Confidentiality will be obtained, because the research could place the subject at risk of criminal or civil liability or cause damage to the subject's financial standing, employability, or liability.

A waiver of documentation of consent is being requested, because the only link between the subject and the study would be the consent document and the primary risk is a breach of confidentiality. (This is not an option for FDA-regulated research.)

- x **Precautions are in place to ensure the data is secure by using passwords and encryption, because the research involves web-based surveys.**

Audio and/or video recordings will be transcribed and then destroyed to eliminate audible identification of subjects.

Subject Confidentiality

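### Trial A has two different primary outcomes: a flu shot at the appointment only, or also shots reported or documented before and after it

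*Protocol*

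**What the plan says.** Protocol, Primary outcome variable(s): "Trial A: The primary outcome is whether participants receive a flu vaccination at their primary care appointment". The Secondary outcome variable(s) field then sets later shots apart: "A secondary outcome is whether participants receive a flu vaccination after their primary care appointment until March 31, 2021".

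The Analysis Plan section of the Protocol opens thus: "For both trials, the primary outcome will be whether participants receive an influenza vaccination, as recorded in their medical records or customer data". It then lists three kinds of event for Trial A. One is a shot at the appointment. The second is "whether they tell their provider they received a vaccination prior to their appointment but after enrollment in our study". The third is "or receive their vaccination at another appointment or location after enrollment in our study (if documented in their medical record"). No end date is given in that section. The model follows directly: "We will use an ordinary least squares (OLS) regression of a binary vaccination receipt indicator at the individual level".

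Protocol, Key exclusion criteria, removes a Trial A patient for an earlier shot only in this case: "Has documentation of already receiving their 2020 influenza vaccination prior to randomization in medical records".

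Other mentions do not decide the matter. The heading on the first page speaks of "text-based nudges encouraging patients to get vaccinated at an upcoming doctor's appointment", but the Protocol Title field on the same page refers only to promoting flu vaccinations. Study Instruments, Overall objectives and Accrual mention flu shots, uptake or vaccination rates without naming a place. The modification summary concerns personnel only.

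**The concern.** The two sections answer different questions. The outcome field asks whether the shot was given at this visit. The Analysis Plan asks whether the patient was vaccinated at all after enrolment, as far as the record shows.

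The first aim of the study is to find which messages work best, so the choice matters for the main result. A message that draws to the visit shots that would otherwise be given elsewhere or later looks stronger under the at-visit definition. A message that prompts people to be vaccinated elsewhere looks stronger under the broad one. The Protocol does not show that either happens, but it leaves open which question the headline estimate answers.

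Timing adds to this. The Protocol version at hand is dated 06/11/2021, after the appointment window closed on March 31, 2021, and it still carries both definitions. A choice made now without a dated record could not be distinguished from one made after seeing the data.

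**Working it through.** **Step 1. Classify patients under each section.** Each row is a Trial A patient with one shot, who was randomised and was not vaccinated again.

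| Shot received | Outcome field: primary | Outcome field: secondary | Analysis Plan: primary |
|---|---|---|---|
| At the appointment (recorded) | event | no | event |
| Between enrolment and the appointment, reported to the provider | no | no | event |
| After the appointment, by March 31, 2021, documented | no | event | event |
| After March 31, 2021, documented | no | no | event, read literally |

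- Row 2 belongs to neither Trial A outcome in the outcome fields. These patients stay in the denominator, because the exclusion covers only shots documented before randomisation.
- Row 3 is the secondary outcome of the outcome fields, absorbed into the Analysis Plan's primary.
- Row 4 arises only because the Analysis Plan gives no end date.

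**Step 2. Relate the two rates.** Suppose every at-visit shot is recorded. Then an Analysis Plan event is an at-visit event or a reported or documented shot outside the visit after enrolment, so within any condition

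p(Analysis Plan) = p(at visit) + p(outside the visit only).

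Taking the difference between a message condition and its comparator,

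effect(Analysis Plan) = effect(at visit) + effect on p(outside the visit only).

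This is an identity and needs no assumed vaccination rate. The last term is the whole gap between the two estimates. It may be positive, negative or zero.

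**Step 3. What can be sized.** Putting a number on the last term needs the share of shots by place and date in each condition, which the Protocol does not give. The only figures for scale are in Accrual: at least 4,000 participants per condition, and a 3% difference to be detected with at least 80% power. Reading the 3% as percentage points, 0.03 × 4,000 = 120 patients in a condition of 4,000. With a comparator of equal size, the two definitions would differ by the full planned difference if outside-only shots differed by 120 patients. This is a yardstick, not an estimate of what happened.

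The stated power cannot be reproduced without a baseline rate, which is not given and would itself depend on the definition. The point does not rest on it.

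**Step 4. Trial B.** Event and place agree between the two sections: a flu shot at a Walmart pharmacy. The window is fall 2020 in the outcome field and open-ended from enrolment in the Analysis Plan. The two can be read together, so this is a matter of wording.

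**The case against.** The strongest reply is that this is loose drafting, not a conflict. The definitions are nested: every recorded at-visit shot counts under both. The outcome field is the form's dedicated place for the primary outcome and deliberately separates shots at the visit from shots after it. The Analysis Plan is a short narrative whose list may simply pool the events to be captured. Alternatively, since the regression sentence directly follows the broad definition, a reader can infer that the regression uses it. Exact windows and documentation rules are often left to a statistical analysis plan, which is not at hand here. Finally, no size is shown, and a change of wording after the window has closed cannot fix the outcome prospectively.

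Several of these points stand:

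- The definitions are nested. The conflict is only that both cannot be the single primary outcome.
- The identity in Step 2 holds only if at-visit shots are all recorded.
- The missing end date is secondary, since March 31, 2021 could be carried over from the secondary outcome.
- The title evidence is mixed, and the Trial B difference is minor.
- No amount of shifting between places, loss of power or change in the ranking of messages has been shown.

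The main reply does not stand. The Analysis Plan uses the label of primary outcome and adds two groups of patients whom the outcome field counts as non-events. If the regression does use the broad indicator, then the analysed outcome is not the one declared in the objectives, which is the same defect seen from the other side. A separate analysis plan might choose between the two, but the Protocol would still state two different primary outcomes. The late date bears on how to repair this, not on whether it needs repair.

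**Conclusion.** The concern holds and must be fixed. The Protocol gives Trial A two different primary outcomes for one binary regression and does not rank them. Patients vaccinated only outside the visit after enrolment, and reported or documented as such, are non-events in one section and events in the other.

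The gap between the two effect estimates equals the message's effect on those outside-only shots, provided at-visit shots are fully recorded. Its sign and size are unknown from the Protocol. The contradiction itself rests on the wording alone and on no assumed rate.

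**What to change.** 1. State one Trial A primary outcome, in identical words, in the Primary outcome variable(s) field and the Analysis Plan. Give the place, the source of documentation, the start at enrolment and a fixed end date.
2. Adopt the definition documented before outcome data were seen, for example in a dated analysis plan or an earlier protocol version, and cite that date.
3. Report the other definition as a named secondary outcome, and adjust the present secondary so that its overlap with the primary is clear.
4. If neither definition can be shown to have been fixed first, report both and say so.
5. State explicitly whether a shot between enrolment and the appointment counts.
6. Minor: word the Trial B window alike in both sections, using the window documented beforehand and not a new cut-off.

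The cost is a change of wording in two sections with the protocol modification this requires, a dated citation, and one extra reported analysis. That analysis uses flu-shot records the trial already obtains (Data Management and Procedures).

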This protocol is for two "mega-studies", in which we will simultaneously test numerous behavioral science strategies to increase flu vaccination rates among Penn Medicine and Geisinger Health primary care patients (Trial A) and Walmart pharmacy customers (Trial B). Our key dependent variable for both trials is whether participants receive a flu shot. For Trial A, Penn Medicine and Geisinger patients with routine (i.e., non-sick) primary care appointments during the Fall 2020 flu season will be randomly assigned to a treatment condition. Patients will be excluded if they: have opted out of text message appointment reminders, have a documented allergy or adverse event to the flu shot, or have already received their 2020 flu shot (documented in their medical record). Intervention content will be delivered via text message to participants from Penn Medicine and Geisinger Health up to four days prior to their scheduled primary care appointments. For Trial B, Walmart pharmacy customers will be included if

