they have consented to receive text messages about their prescriptions and have received a flu shot from Walmart in the past. Intervention content will be delivered via text message to Walmart pharmacy customers at the start of the flu season. Between Trial A and Trial B, we plan to include at least 40 different experimental conditions designed by the Behavior Change for Good Scientific Team (including researchers at Penn and other institutions), by Geisinger employees, and by Walmart employees. Interventions may vary the content and timing of text messages (including whether messages are interactive or provide links to surveys and videos). Interventions may also include incentives for behaviors of interest (e.g., receiving the flu shot or completing a survey), the details of which would be described in the text messages themselves. Details of each experimental condition have been included as a separate attachment as a modification to this protocol. Text messages may include first name, appointment date and time, provider name, and practice/pharmacy locations. This is in line with the standard appointment reminders that Penn Medicine patients receive, which includes first name, appointment date and time, and department information. Specifically, the Penn Medicine reminders say "PENNMED: (First Name) has an appt (APPT Date /Time)@(SMS Department Abbreviation). To confirm txt YES. To decline txt NO. Txt Help 4help." Any additional information that we include in text messages to participants beyond that does not include HIPAA information. All messages will be reviewed and approved by our partners before being launched.

Group Modifications

Describe necessary changes that will or have been made to the study instruments for different groups. The content and timing of text messages and incentives will vary according to which intervention participants are assigned. Specific messages and incentive information has been added as a modification.

Method for Assigning Subjects to Groups

Describe how subjects will be randomized to groups.

In Trial A, patients will be randomly assigned to experimental conditions using stratification that accounts for demographics (e.g., age), and recruitment site. Trial B will also randomly assign participants to experimental conditions, and may also use stratification that accounts for demographics (e.g., age).

Administration of Surveys and/or Process

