For Trial A, intervention content will be delivered to participants via text messages from the WayToHealth platform. Penn Medicine and Geisinger will provide the patient data and appointment data needed for WayToHealth to deliver the interventions. This may include a unique identifier, medical record number, first and last name, address, appointment date, appointment time, appointment type, practice and physician information, patient town and zip code, date of birth, gender, phone number(s), documented allergy to the flu shot, and documentation of flu shot receipt for the 2020 flu season. Penn Medicine and Geisinger will also indicate which phone numbers have opted out of receiving text message reminders. WayToHealth will receive these data from Penn Medicine via a secure data feed and from Geisinger via a secure upload. There will be data use agreements in place governing the data sharing with WayToHealth and Wharton as required. The Penn Medicine Academic Computing Services (PMACS) will be the hub for the hardware and database infrastructure that will support the project and is where the WayToHealth web portal is based. The PMACS is a joint effort of the University of Pennsylvania's Abramson Cancer Center, the Cardiovascular Institute, the Department of Pathology, and the Leonard Davis Institute. The PMACS provides a secure computing environment for a large volume of highly sensitive data, including clinical, genetic, socioeconomic, and financial information. Among the IT projects currently managed by PMACS are: (1) the capture and organization of complex, longitudinal clinical data via web and clinical applications portals from cancer patients enrolled in clinical trials; (2) the integration of genetic array databases and clinical data obtained from patients with cardiovascular disease; (3) computational biology and cytometry database management and analyses; (4) economic and health policy research using Medicare claims from over 40 million Medicare beneficiaries. PMACS requires all users of data or applications on PMACS servers to complete a PMACS-hosted cybersecurity awareness course annually, which stresses federal data security policies under data use agreements with the university. After the end of the intervention, patient and intervention data will be transferred from WayToHealth, Penn Medicine, and Geisinger to the Leonard Davis Institute's Health Services Research Data Center (HSRDC), which is maintained at a high security level in accordance with federal regulations (e.g., HIPAA) governing secure computer systems. This will include all data used for study implementation (i.e., the full list included above), as well as additional data to be used in analysis. The additional data may include patient diagnosis, procedures, and prescription information from the previous 5 years, marital status, and whether they have children, race/ethnicity, Charlson Comorbidity score, insurance type, a record of previous flu vaccinations from the previous 5 years, a record of all doctor visits in the past year, appointment arrival time, preferred pharmacy, number of emergency contacts and relation to emergency contacts, patient body mass index, smoking status, record of prior positive test for the flu, and primary care physician (PCP) specialty. Storage and analysis protocols for the data on the LDI HSRDC will be included in the data use agreement with Geisinger and Walmart. All identifiable data will be removed from this list as soon as possible, and will not be used for analysis. The Geisinger investigators will have access to data on (1) any intervention(s) they design, and (2) intervention data for Geisinger patients across all interventions for the purpose of running internal analyses through the HSRDC. They will handle all data in accordance with Geisinger and IRB policies. For Trial B, Walmart pharmacy will deliver the interventions directly to eligible Walmart pharmacy customers via their own text messaging platform. At the end of the intervention, Walmart pharmacy will transfer intervention data (e.g., to which intervention each customer was assigned, text messages sent and received) along with customer pharmacy and medical data (e.g., whether they received a flu shot, previous medical diagnoses) and customer demographic data (e.g., age, gender) to the HSRDC for analysis. Identifiable data will not be shared. For both Trial A and Trial B, collaborators at Penn and other institutions will access and analyze the non-identifiable data on participants assigned to the interventions they designed through the HSRDC. The server does not allow data to be copied or moved off of the server. Access will only be granted to investigators at other institutions after a data use agreement with Penn has been executed.

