For Trial A, Penn Medicine and Geisinger patients with scheduled primary care appointments during the Fall 2020 flu season who receive SMS reminders of their appointments from their health system will be randomly assigned to receive one of the SMS interventions. For Trial B, all eligible Walmart pharmacy customers will be randomly assigned to receive one of the SMS interventions. In both trials, participants will receive text messages with the content and timing varying based on the intervention design. For Trial A, patient and appointment data (including patient name, telephone number, zip code and town of residence, age, and gender, appointment date, time, and type, practice name and location, information about the primary care physician, and a record of whether they received the flu shot) from Penn Medicine and Geisinger, will be shared with WayToHealth on a regular basis for study implementation (e.g., to randomize participants to condition, deliver intervention content and incentives). After study completion, identifiable information will be removed from the data. WayToHealth will transfer the patient and appointment data, in addition to all intervention data (e.g., text messages sent and responses received), to LDI HSRDC for storage and analysis. Penn Medicine and Geisinger will also transfer additional patient information (e.g., records from previous appointments, comorbidities, additional demographic information) to LDI HSRDC for analysis. For Trial B, interventions will be implemented on Walmart's own text messaging platform. Data will be shared with LDI HSRDC for storage and analysis after the end of the study. This data will include intervention data (e.g., intervention assignment, text messages sent and responses received) and pharmacy information (e.g., flu shot receipt, medical diagnoses) and customer demographic data (e.g., age, gender) from Walmart pharmacy records.

The following documents are currently attached to this item:

There are no documents attached for this item.

Deception

Does your project use deception?

No

International Research

Are you conducting research outside of the United States?

No

Analysis Plan

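### Trial B could carry Trial A's exclusion for a recorded flu-vaccine reaction: a cheap, low-severity safety-consistency fix

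*Protocol*

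**What the plan says.** **Trial A.** The protocol's Key exclusion criteria list "Has documentation of allergy or adverse event to influenza vaccination in medical records". The design summary under Study Instruments repeats the rule for patients who "have a documented allergy or adverse event to the flu shot". Data Management names flu-shot allergy among the fields that Penn Medicine and Geisinger supply so that the texts can be delivered.

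**Trial B.** Key exclusion criteria gives the single word None. Key inclusion criteria sets three conditions: consent to prescription texts, "Have received a flu shot from Walmart in the past", and being chosen for the study by Walmart. Subject recruitment then says "All eligible Walmart pharmacy customers will be enrolled and randomly assigned to a study condition", and Procedures agrees: "For Trial B, all eligible Walmart pharmacy customers will be randomly assigned to receive one of the SMS interventions". On incentives, Study duration says of Trial B customers: "They may also receive additional messages about incentives earned after receiving a flu shot". Data Management names no allergy field for Walmart.

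**Risk.** Potential Study Risks and Risk / Benefit Assessment acknowledge that the shot can have side effects and reply that subjects could get it without the study. Minimal Risk adds that Trial B takes only customers who already get Walmart pharmacy texts. Impact on Subject Rights and Welfare adds that subjects may decline the shot. Consent is waived.

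**The concern.** Both trials text people to raise uptake of the same vaccine, and receipt of it is the primary outcome in both. In Trial A a recorded reaction to that vaccine stops the prompt; in Trial B it does not, and the protocol gives no reason for the difference.

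The protocol also does not say why Trial A has the exclusion. It may be for safety, or because a prompt serves no purpose for someone who should not have the shot. Either reason would cover a Trial B customer whose reaction is on record. With consent waived and no additional information given to participants, the written eligibility rules carry more of the protection than they otherwise would. What is at stake is the consistency of a safety rule. Bias and power are not affected.

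**Working it through.** The point is textual and has no figure in the plan to reproduce. The check sets the two eligibility rules side by side, then bounds the size of the gap and the cost of closing it.

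**1. The rules compared**

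| Element | Trial A | Trial B |
|---|---|---|
| Vaccination prompted by text | Yes | Yes |
| Incentive for the shot possible | Yes | Yes |
| Past flu shot required | No | Yes, at Walmart |
| Recorded allergy or adverse event excluded | Yes | No |
| Allergy field named for delivery | Yes | No |

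**2. Who stays eligible in Trial B**

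- Known allergy, never vaccinated: removed by the past-shot criterion.
- Vaccinated at Walmart without a reaction: no issue.
- Vaccinated at Walmart, reacted, reaction not recorded: a records-based rule would miss this person in either trial.
- Vaccinated at Walmart, reacted, reaction recorded: meets the past-shot criterion and is removed by no stated rule. A Trial A patient with the same entry in the medical record is excluded.

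Only the last group separates the two trials.

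**3. Size of the group.** The protocol gives no rate of recorded reactions, so only a conversion is possible. The planned Trial B size is 1.0 million under Accrual and about 1.2 million in the Abstract. The latter agrees with the collaborating-site total less Geisinger: 1,275,000 − 75,000 = 1,200,000. Actual enrolment at participating centres is given only as a combined 772,628, so planned sizes are used.

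- Per 1 in 10,000: 1,000,000 / 10,000 = 100; 1,200,000 / 10,000 = 120.
- Over an assumed range from 1 per million to 1 per 1,000: from 1,000,000 × 0.000001 = 1 to 1,200,000 × 0.001 = 1,200.

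These rates are assumptions, not estimates. If Walmart holds no such records, the number is zero.

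**4. Cost in sample.** Removing a share f of customers multiplies standard errors by 1/√(1 − f). At an illustrative f = 0.01 this is 1/√0.99 = 1.005, a rise of 0.5%.

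Accrual's power statement (at least 80% power for a 3% difference) is tied to a floor of 4,000 per condition. The protocol plans at least 40 conditions over both trials and does not say how many are in Trial B. If 40 were all in Trial B, equally sized:

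- Before removal: 1,000,000 / 40 = 25,000 per condition.
- After removing 1%: 25,000 × 0.99 = 24,750 per condition.

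Both are far above 4,000. With 1.0 million customers the floor is reached only at 1,000,000 / 4,000 = 250 conditions. The power statement does not change.

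**The case against.** The strongest reply is that the two pools differ. Trial A is open to people who have never been vaccinated, perhaps because of a known allergy; Trial B takes only people who have had the shot. Different entry rules can justify different exclusions. This stands in part: the gap is narrower than the two lists suggest. It does not close it, because the criterion asks nothing about how the shot was tolerated.

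Second, the lists may follow the data. The protocol names no Walmart allergy field, and the Walmart data it does describe, "customer pharmacy and medical data (e.g., whether they received a flu shot, previous medical diagnoses", are transferred after the intervention, for analysis. This stands as a limit on how much the fix can do.

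Third, Walmart's own selection might screen for reactions, and a list of key exclusions need not be exhaustive. That is possible, but no selection rule is stated, so no screen can be credited.

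Fourth, the risk is small: the study gives no vaccine, Trial B customers already receive Walmart texts, and they may decline the shot. This stands, and it is why the point is minor. But access to the shot and freedom to decline hold in Trial A too, where the exclusion was still written, so they do not explain the difference.

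A reader might go further and infer that customers with known reactions were texted or harmed, or that the minimal-risk finding is unsound. The protocol supports neither. It does not show that any such customer exists in Walmart's records or was selected, and its minimal-risk argument rests mainly on the likeness of the messages to usual pharmacy texts.

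**Conclusion.** The point holds as a low-severity improvement. As written, a recorded reaction to influenza vaccination bars a person from Trial A but not from Trial B, although both trials prompt the same shot and either may reward it. The past-shot criterion reduces the gap without closing it.

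The number of customers concerned is unknown and may be zero. No figure, estimate or test in the plan is wrong on this account. The conclusion assumes only that the stated Trial B criteria are the ones applied; a documented Walmart screen for reactions would answer it.

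The practical reach is limited. Trial B's messages were planned over 4 days at the start of the flu season, this version is dated 06/11/2021, and no further Trial B wave is planned. The point therefore concerns the eligibility rule as written.

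**What to change.** Under Key exclusion criteria, replace the Trial B entry None with a line such as: *a recorded allergy or adverse reaction to an influenza vaccine in Walmart's pharmacy records, where such a record exists*. Apply it as a filter when Walmart builds the customer list. If Walmart cannot apply it, or already screens, one sentence saying so would serve.

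The cost is one line of text, one list filter and a negligibly smaller Trial B sample. The filter would miss reactions that Walmart's records do not hold, and would remove nobody if they hold none.
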